#### Randomization and blinding

The use of 2:1 randomization (NT 201 or placebo) in the main period and the migration to all-active treatment in the extension period has been chosen in order to keep the number of subjects treated with placebo as small as possible.

The double-blind, placebo-controlled, randomized, multi-center design of the main period has been chosen to allow the acquisition of scientifically robust efficacy and safety data on NT 201 in children and adolescents with chronic troublesome sialorrhea due to neurological disorders – data that will not be biased by the subject or the investigator. A superiority study with a placebo control allows valid conclusions about efficacy and safety and safety and represents the state of the art in this kind of clinical research.

Currently, no pharmacological agents have FDA or EU approval for treatment of sialorrhea in adults. For pediatric patients, there is currently only one pharmacological agent approved by the FDA for chronic severe sialorrhea (Cuvposa (glycopyrrolate) Oral Solution [NDA 022571]). This is an anticholinergic indicated to reduce chronic troublesome drooling in patients aged 3–16 years with neurological conditions associated

with problem drooling (e.g., cerebral palsy). The use of this agent is compromised by the occurrence of dose-limiting constipation and drowsiness, both of which already can be problematic in CP. Additionally, Cuvposa has other anticholinergic drug effects which may limit its use in patients with coronary heart disease, congestive heart failure, and cardiac tachycardia. Cuvposa is administered as an oral solution. Therefore using it as a comparator in this study would compromise the blinding and it could only be implemented by a double-dummy design, meaning that both the NT 201-treated group and the control group would need to receive the oral solution (placebo or active treatment) and the injection (active treatment or placebo, respectively) at the same time. This would lead to higher risks for subjects than the pure placebo control.

As no substance has yet received marketing approval for the treatment of chronic troublesome sialorrhea for minors in the EU, and to date no appropriately powered pivotal study data on *Botulinum* toxin in this indication are available, therefore placebo treatment in about 33% of all enrolled and randomized subjects (age 6–17 years) for one single injection cycle during the main period out of a total of four injection cycles is justified. All children age 2–5 years will receive NT 201 in the main period. However, it was also considered to be important not to withhold treatment from subjects needing it in this burdensome indication. Therefore, the placebo group in the main period was kept small, and the extension period (required by the need for long-term safety data) was designed without placebo treatment. All subjects will receive active treatment during the extension period. All subjects are expected to benefit from treatment with NT 201 (subjects in the placebo group three times, subjects in the active treatment group four times).

Following discussions with the relevant regulatory authorities, it was considered necessary to follow at least 100 children treated with clinically relevant doses of NT 201 continuously for one year. At least 50 of these patients must have received the high dose (at least 2 U/kg body weight) consistently for one year (series of four injections). The safety database requirement in children for cumulative exposure at six months is also at least 100 subjects treated consistently with clinically relevant dosages for two injections.

#### Duration of treatment and assessment

The length of each injection cycle was chosen on the basis of reported observations that the effect of *Botulinum* toxin builds up over approximately two weeks after treatment and decays after 8–12 weeks [Chinnapongse 2012, ClinicalTrials.gov 2011]. Therefore, in order to avoid any unwanted reinforcement of consecutive doses, a separation of 16 weeks (at least 14 weeks) between doses was incorporated into the design.

Sialorrhea manifesting itself as a consequence of neurological disease is a chronic health problem and requires long-term treatment. Therefore, the extension period of this study investigates the efficacy and safety of repeated administration of NT 201, given at fixed intervals. Following the placebo-controlled main period of  $16\pm 2$  weeks' duration, all subjects complying with the eligibility criteria will receive active treatment in the extension period. Each subject will receive at least three injections with NT 201 within an overall treatment period of 64 weeks.

#### Recruitment strategy based on safety monitoring

The staggered recruitment described in the following section will give early warning if any unexpected safety issues arise. Depending on the results of the (numerous) safety reviews, the design of the study may be modified by discontinuing recruitment, either for the next younger age group or completely. Details are set out in the following section.

## 6.3 Recruitment strategy

This international study is planned to be performed in eligible investigational sites in about 40 centers in European Union (EU) and outside of the EU (e.g. Poland, Hungary, Romania, Georgia, Turkey, Serbia, Ukraine and Russia). The selection of countries and centers was performed on the basis of the outcome of a feasibility survey. A conservative staggered recruitment procedure will be applied in order to minimize potential age-related risks for the participating children and adolescents. This comprises the steps set out below, in which reference is made to the age groups defined in Table 1.

Step	Age 10–17 inclusive	Age 6–9 inclusive	Age 2–5 inclusive	j	Cohort nı initial DN	umber fo IC reviev	r V
1	30 subjects	—	-	1	2		
2	30 subjects	_	_		2	3	
3	Continuous recruitment	30 subjects	-				4
4	Continuous recruitment	Continuous recruitment	30 subjects				
Random- ization?	Yes	Yes	No				
Treatment in main period	Double placebo-c	e-blind, controlled	Open, active treatment only				

Table 1:Overview of age groups and recruitment steps

#### Step 1

In the first recruitment period, 30 children/adolescents (10–17 years of age) will be recruited (cohort 1). These subjects will be randomized and treated with either NT 201 (active treatment) or placebo (randomization ratio 2:1) during the double-blind main period.

Safety data acquired from this cohort will be reviewed by the DMC when 4 weeks elapsed after the last subject of the cohort was randomized.

# Step 2

If in the above analysis no significant risk is identified by the DMC, then a second set of 30 children/adolescents (10–17 years of age) will be recruited, randomized and treated in the same manner as the first 30 subjects (cohort 2).

Safety data acquired from cohorts 1 and 2 will be reviewed by the DMC when 4 weeks elapsed after the last subject of cohort 2 was randomized.

# Step 3

If in the above analyses no significant risk is identified by the DMC, then a further group of 30 younger children (6–9 years of age) will be recruited, randomized and treated (cohort 3).

In parallel with this, recruitment and treatment of subjects in the age group 10–17 years will continue.

Safety data acquired from all subjects randomized hitherto  $(N \ge 90)$  will be reviewed by the DMC when 4 weeks elapsed after the last subject of cohort 3 was randomized.

# Step 4

If in the above analyses no significant risk is identified by the DMC, then a further 30 children representing the youngest age group (2–5 years of age) will be enrolled (cohort 4). Children in this youngest age group will not be treated with placebo, but only with active treatment (NT 201) during all four injection cycles.

In parallel with this, recruitment and treatment of subjects in the older two age groups will continue.

## Termination of recruitment

Recruitment will continue in the age groups covering the age range from 6 to 17 years inclusive until the target number of 219 subjects randomized and treated is reached. Recruitment in these age groups will then stop.

Recruitment will continue in the age group 2–5 years inclusive until the target number of 30 subjects treated is reached. Recruitment in this age group will then stop.

If recruitment in one or another group is unexpectedly or disproportionately slow, then the sponsor has the right to terminate recruitment before the respective target number is reached. The sponsor also has the right to terminate recruitment, overall or in a given age group, by recommendation of the DMC for safety-related reasons.

With the recruitment strategy described above, and assuming that no premature termination of recruitment takes place as outlined above, a total of 249 subjects will be enrolled and treated; of these, 30 will have received active treatment without randomization, 219 will have been randomized to receive either active treatment (146 subjects) or placebo (73 subjects) in the main period. All study subjects will have received NT 201 in the extension period.

#### Period of recruitment

It is estimated that recruitment will commence in the first quarter of 2015 and will be completed during the first quarter of 2018. The end of the study (final study visit by the last subject) would then be in the second quarter of 2019.

# **7** STUDY POPULATION

# 7.1 Selection of study population

Study subjects (male and female children and adolescents in the respective age groups) will be recruited according to criteria determined by having a relevant medical condition of chronic troublesome sialorrhea associated with neurological disorders and/or intellectual disability requiring study treatment, and by having no medical condition or other circumstance that might interfere with the conduct or result of the study or endanger a subject's safety.

## Distribution of gender

As the study indications are not gender-specific, no stratification or selective recruitment of male/female subjects will be performed. It is assumed that the accrual of male and female subjects without distinction at all investigation sites will in itself lead to a balance of the genders that will be adequate for the study analysis.

## 7.2 Inclusion criteria

Only individuals meeting all of the following inclusion criteria, at screening and/or at baseline as indicated, will be considered for study enrollment:

	Inclusion Criteria	Ratio- nale	Scr	BL
1.	Written informed consent obtained from the child's/adolescent's parent(s) and oral or written assent by the child/adolescent (following information to the extent compatible with the subject's understanding if applicable).	Adm	X	
2.	Male or female child/adolescent aged 2 to 17 years (i.e., second birthday reached, and eighteenth birthday not yet reached, on the date of first administration of study medication).	Adm	X	X
3.	Understanding of study procedures and willingness to abide by all procedures during the course of the study by the parent(s) and/or the child/adolescent (if applicable).	Adm	X	

	Inclusion Criteria	Ratio- nale	Scr	BL
5.	Any neurological disorder (e.g. cerebral palsy or traumatic brain injury) and/or intellectual disability associated with chronic troublesome sialorrhea for at least 3 months up to the screening. In subjects with intellectual disability (ID) without neurological disorders, a diagnosis of ID by a specialist, e.g. pediatrician or by a center for developmental medicine is required for inclusion.	Ind	Х	
6.	mTDS of $\geq 6$ (= severe drooling to the extent that clothing becomes damp occasionally) rated by the investigator.	Ind	Х	X
7.	Female subjects of child-bearing potential a must be using a highly effective method of birth control <math>b</math> .	Safety	X	X

*a* Any female who has experienced menarche and is not permanently sterilized (e.g. tubal occlusion, hysterectomy, bilateral salpingectomy).

*b* Defined as a method that results in a low failure rate (i.e., less than 1% per year) when used consistently and correctly, such as implants, injectables, combined oral contraceptives, sexual abstinence, or vasectomised partner.

Screening [Scr]; baseline [BL]; administrative [Adm]; definition of the study indication [Ind].

Note: The technical prerequisite for inclusion of subjects is the confirmation through the IWRS [interactive web response system] that the study is currently recruiting in the age group of the child/adolescent.

## 7.3 Exclusion criteria

Individuals meeting any of the following criteria, at screening or at baseline as indicated, will not be included in the study:

	Exclusion Criteria	Ratio- nale	Scr	BL
1.	Diagnosis of chronic troublesome sialorrhea not related to a neurological disorder and/or intellectual disability, e.g. malformation of the salivary ducts or glands.	Int	Х	
2.	Subject with body weight < 12 kg.	Safety	X	Χ

	Exclusion Criteria	Ratio- nale	Scr	BL
4.	Aspiration pneumonia within 6 months before screening.	Safety	Х	Χ
7.	Prior, concomitant or planned surgery or irradiation to head and neck to control sialorrhea (including salivary gland surgery or salivary gland irradiation) within one year before screening or planned for any part of the entire study period.	Int	X	X
9.	Any previous treatment with Botulinum toxin for any body region during the year before screening or within the screening period.	Int	X	X
11	. Known or suspected hypersensitivity to either Botulinum toxin (any serotype) or any ingredient of the formulation or analgesics or sedatives (used for premedication for analgosedation or anesthesia).	Safety	X	X
12	Extremely poor dental and/or oral condition that might preclude safe study participation by the judgment of the investigator.	Int	X #	X

Exclusion Criteria	Ratio- nale	Scr	BL	
16. Pharmacological treatment for sialorrhea or concomitant medication known to influence sialorrhea strongly (e.g. anticholinergics with exception of locally applied or short acting drugs used under general anesthesia) within 45 days before baseline and during the entire study period.	Int	X	Х	
18. Concurrent diseases, including hematological, hepatic, renal, gastrointestinal, endocrine, pulmonary, musculoskeletal, or psychiatric diseases or conditions, which in the judgment of the investigator would put the subject at risk while in the study, could influence the results of the study, or negatively impact the subject's ability to participate in the study	Safety	Х	Х	
19. Nursing mother or pregnant female subject.	Safety	X	Х	

Exclusion Criteria	Ratio- nale	Scr	BL	

Screening [Scr]; baseline [BL]; risk of interference with study objectives [Int]; administrative [Adm]; (\*) to avoid unnecessary distress to the subject; #dental examination by dentist needs to be performed until baseline visit.

# 7.4 Eligibility criteria for continued treatment in the extension period

Criteria for the transition to the extension period (V6/6a) and for continued treatment within the extension period (V10/10a and V14/14a) are listed below. (Note that the pairs of visits 6/6a, 10/10a and 14/14a will normally take place on the same respective day.)

If these eligibility criteria are not fulfilled at the end-of-cycle visit postponement of study treatment may take place at the beginning of the following injection cycle of the extension period. The re-injection visit can be postponed for up to a maximum of two weeks (but no longer than 18 weeks after the preceding treatment visit). For subjects who still do not fulfill the eligibility criteria at the revisit, study participation will be ended.

	Eligibility Criteria for Extension Treatment	Ratio- nale	Visits 6, 6a, 10, 10a, 14, 14a
1.	Clinical need for re-injection.	Ind	Х
2.	Absence of medically-relevant severe adverse events of special interest that are judged to have a causal relationship to the study treatment (indicative of toxin spread in the area of injection), especially respiratory arrest/distress/failure and dysphagia necessitating diet changes occurred during any period of the study.	Safety	Х
3.	No concomitant infection or inflammation in the head and neck region.	Safety	Х

Page 52 of 183

		Eligibility Criteria for Extension Treatment	Ratio- nale	Visits 6, 6a, 10, 10a, 14, 14a
4.	Neg fem	ative result of pregnancy test (testing only performed for ale with history of menarche, i.e. the first menstrual bleeding).	Safety	Х
5.	No :	significant risk of suicidality since last injection based on the Investigator's judgment, and	Safety	Х
	•	if appropriate, as indicated by a response of "no" to questions 4 or 5 in the suicidal ideation section of the C-SSRS		
	•	and no non suicidal self-injurious behavior		
	•	and no suicidal behavior.		

Definition of indication for continued study treatment [Ind]; administrative [Adm].

## 7.5 Removal of subjects from treatment or assessment

## 7.5.1 Discontinuation of subject's study participation

In accordance with the Declaration of Helsinki and the informed consent form, the subject or his/her parent(s) may discontinue the subject's participation in the study at any time without any penalty or loss of benefits to which the subject is otherwise entitled (see Section 7.5.3). Both the premature withdrawal from the study and the reason(s) for this are to be recorded in the subject's file and the eCRF. The date and circumstances of the discontinuation should be stated.

Subjects are to be withdrawn from the study by the investigator at any time if any of the following occurs:

- Withdrawal of informed consent.
- Pregnancy (no further administration of NT 201, blood sampling, or any other interventional or invasive procedure will be performed).
- Any AE for which treatment continuation would constitute an unacceptably high risk for the subject.
- Any eligibility criteria for reinjection are not met within 18 weeks after the previous injection of IP in the respective injection cycle (MP or OLEX).

- AESIs of severe intensity that represent respiratory function disorders or swallowing disorders will trigger the premature termination of a subject without reexposition to IP. The terms for these severe AESIs are:
  - AESI terms related to respiratory function disorders are aspiration, diaphragmatic paralysis, dyspnoea, pneumonia aspiration, respiratory arrest, respiratory depression, and respiratory failure.
  - AESI terms related to swallowing disorders are bulbar palsy, multiple cranial nerve palsies, dysphagia, hypoglossal nerve paresis, cranial nerve paresis, cranial nerve paralysis.
- Positive report on suicidality of subject (C-SSRS answer "yes" to questions 4 or 5 or any suicidal behavior) or non-suicidal self-injurious behavior.

Deviations from this clinical study protocol, or conditions arising from the exclusion criteria as set out in Section 7.3, may (but will not necessarily) lead to the subject's withdrawal. All such conditions are to be properly documented. In such cases, the decision on whether or not to withdraw the subject will be made by the investigator in consultation with the sponsor, taking principally the safety of the subject into account.

Subjects who are withdrawn from the study because of AEs will be treated by standard clinical methods and will be followed up until (and including) the last scheduled visit of the injection cycle in which they were withdrawn or until 28 days after the onset of the adverse event, whichever date is the later. All pertinent information concerning the AE will be documented in the subject's hospital medical file as well as in the eCRF AE report form.

Following a subject's withdrawal, a final examination should be performed for safety reasons if parents/carers are willing to bring the child for the visit. The investigator is required to make every effort to contact subjects lost to follow-up, and all such efforts are to be documented in the subject's hospital medical file (e.g., times and dates of telephone contact, copies of letters).

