#### **End-of-study visit**

This will be the same as the end-of-cycle visit for the fourth injection cycle (above). Subjects who withdraw, or are withdrawn, prematurely from the study will be requested to attend for this final examination.

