### 12.1.2 Efficacy

Subjects in age group 6-17 years

The sample size of 219 subjects is sufficient to provide 95% power to detect a statistically significant difference in means of 1.0 point between active treatment-treated and placebo-treated subjects with a standard deviation of 1.93 points (two-sided *t* test, significance level  $\alpha = 0.05$ ).

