### 12.4.1.1 Primary efficacy variables

The primary efficacy analysis will be performed on the group of subjects within the FAS aged 6–17 years. A mixed model repeated measurement analysis (MMRM, 2-sided, significance level alpha=0.05) with comparison of least square means between NT 201 and placebo will be used for the confirmatory analysis of the co-primary efficacy variables. The dependent variables will be the change in uSFR from baseline (V2) to V3 [Week 4] and the carer's/parent's GICS at V3 [Week 4], respectively. The independent variables are defined as treatment group, pooled investigation sites and age groups as fixed factors, visit\*treatment as interaction term, and visit as repeated factor. To adjust for the baseline status, the MMRM of the uSFR change additionally includes the baseline score of the uSFR as covariate. Since no baseline assessment of the GICS is available, the baseline mTDS rated by the parent(s)/carer is used as covariate in the MMRM model for the GICS. Only if both co-primary efficacy variables show a statistically significant difference compared to placebo the superiority of NT 201 over placebo will be considered to be proven. Therefore, no  $\alpha$ -adjustment for multiple testing is necessary.

Sensitivity analyses will be performed using the same approach on the PPS.

In order to investigate the impact of missing values and different approaches for handling of missing data, sensitivity analyses will be performed on the FAS (age 6-17 years) and on the PPS using the baseline observation carried forward approach (BOCF, no effect) for uSFR while imputing missing GICS entries at week 4 as "no change" and without missing replacement (observed case analysis). For this purpose the MMRM model as described above will be adapted as an analysis of covariance (ANCOVA) model without visit\*treatment as interaction and without visit as repeated factor.

Furthermore, a non-parametric Wilcoxon rank-sum test will be performed as sensitivity analysis of the co-primary efficacy variables to investigate the impact of potential deviations from the assumption of normal distribution. The test will be performed for FAS (age 6-17 years) and PPS using observed cases as well as using BOCF for uSFR and imputing "no change" for GICS.

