## 12.4.7 Special statistical/analytical issues

### 12.4.7.1 Discontinuations and missing data

Reasons for premature discontinuation by a subject will be summarized descriptively and listed. Where the discontinuation was due to an adverse event, this will be included in the listing of adverse events, and such events will be included as a category in the summary of adverse events.

The analysis of the primary and secondary efficacy variables will be performed using a MMRM as well as using an ANCOVA based on observed cases and an ANCOVA with missing values replaced by the baseline value or "no change" ('baseline observation carried forward approach'). By using all values of the dependent efficacy variable available in the timeframe underlying the MMRM, i.e. the main period, the MMRM reduces the influence of single missing values. The use of the ANCOVA model with missing values replaced by the baseline value is considered to be a conservative approach because if a comparable percentage of missing values is expected in both treatment groups (in the placebo group there may be more missing values due to lack of efficacy and in the verum group more due to adverse events) the replacement of missing values by the baseline value of the uSFR – or by 'no change' for the GICS – leads to a decrease in the difference of the observed treatment effects (see also Section 12.4.1.1).

If a subject is not able to answer (documented in the eCRF) then the result of the subject's GICS entry will be replaced by the result of the carer's GICS entry. If it is not documented in the eCRF that the subject is not able to answer then the subject's GICS entry will not be replaced by the carer's GICS entry.

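### In the single-injection main period, the adverse-event stopping criteria end study participation, and no available text requires the Week 4 co-primary assessments afterwards

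*Protocol*

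**What the plan says.** The Synopsis describes the main period as one treatment followed by 16 weeks of assessment. Protocol 6.1.2 puts V3 at Week 4, V4 and V5 at Weeks 8 and 12, and V6 at Week 16 ± 2 weeks. The next injection is not due until V6a. Both co-primary variables are read at V3 (12.3.1.1).

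Section 7.5.1 introduces its criteria with "Subjects are to be withdrawn from the study by the investigator at any time if any of the following occurs". The adverse-event (AE) criterion is framed by the risk of continuing treatment. For severe adverse events of special interest (AESIs) the text is: "AESIs of severe intensity that represent respiratory function disorders or swallowing disorders will trigger the premature termination of a subject without reexposition to IP".

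What follows a withdrawal is described in four places:

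- 7.5.1: children withdrawn for AEs are "followed up until (and including) the last scheduled visit of the injection cycle in which they were withdrawn", or to 28 days after AE onset if that is later. The text concerns AE documentation. A final examination is wanted for safety reasons.
- 6.1.2, End-of-study visit: "Subjects who withdraw, or are withdrawn, prematurely from the study will be requested to attend for this final examination".
- 9.2: stopping study treatment early leads to an end-of-study assessment, then safety follow-up by telephone or in clinic if needed.
- 10.1: after discontinuation the final visit falls 16 ± 2 weeks after the last administration.

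None of these mentions uSFR or GICS at V3–V5. Table 6 is not in the text available.

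On the analysis side, the FAS is everyone treated in the main period (12.2). The confirmatory model ("MMRM, 2-sided, significance level alpha=0.05") is run on FAS children aged 6–17, with no imputation stated. Section 12.4.7.1 argues that "the MMRM reduces the influence of single missing values". ANCOVA and Wilcoxon sensitivity analyses also use baseline or no-change replacement. SAP 7.1.1 leaves intercurrent events to the blind data review meeting. SAP 7.1.2 brings V6 values into the MMRM.

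**The concern.** Once the Day 1 injections are given, a main-period stopping criterion can affect only later injections. The protocol has no status for a child who is off treatment but still on study, so the criterion also ends participation. If that happens before V3, following the stated rules can forgo a Week 4 value that could have been measured at an already scheduled visit.

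The main estimand in SAP 7.1.1 covers treated subjects. Children who stop early because of an adverse event belong to that population, and they are unlikely to be a random sample of it. Protocol 12.4.7.1 itself allows that missing values may arise more from AEs on NT 201 and more from lack of efficacy on placebo. An MMRM without these children compares those who remained. A decision at the blind data review meeting cannot recover assessments that were never made.

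**Working it through.** **1. Which criteria in 7.5.1 can act before V3?**

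- AE with unacceptable risk, and severe AESI: yes. AESIs are actively asked about at visits, V3 being the first scheduled one, so an earlier withdrawal needs an earlier report.
- C-SSRS or self-injury: the first scheduled post-baseline assessment is V3 (10.7), so only through an unscheduled visit or report.
- Re-injection eligibility: no. It is judged at V6 or later.
- Pregnancy: possible, but 10.6 then limits activity to end-of-study checks and assessments.
- Consent withdrawal: possible, but not a criterion about re-injection.

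A withdrawal after V3 does not remove the V3 value.

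**2. The plan's own power.** Protocol 12.1.2: "The sample size of 219 subjects is sufficient to provide 95% power" for a "difference in means of 1.0 point between active treatment-treated and placebo-treated subjects with a standard deviation of 1.93 points", with 146 and 73 children.

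- SE = 1.93 × √(1/146 + 1/73) = 0.2767.
- Normal approximation: Φ(1.0/0.2767 − 1.96) = 95.1%. Noncentral t: 94.9%. The stated 95% reproduces, with no allowance for missing Week 4 values.

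**3. Precision cost.** The documents give no pre-V3 loss rate. Protocol 12.1.1 goes from 144 children to 100 over one year, which implies 1 − 100/144 = 30.6%. Spread evenly this is 1 − (100/144)^(1/4) = 8.7% per cycle over four cycles, or 1 − (100/144)^(1/3) = 11.4% over three. That is all-cause attrition and cannot be read as loss before Week 4. The shares below are therefore assumed, equal in both arms (noncentral t):

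| Lost before V3 | Power |
|---|---|
| 0% | 94.9% |
| 2% | 94.5% |
| 5% | 93.9% |
| 10% | 92.7% |
| 20% | 89.5% |

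Power reaches 90% at about 19% loss.

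**4. Does a later value keep the child in the MMRM?** Take four visits and an assumed common correlation of 0.5. At 5% loss (7 NT 201, 4 placebo), the SE of the Week 4 difference is 0.2842 if these children have no value and 0.2823 if they have V6 only. Power is 94.0% against 94.3% (normal approximation). A V6-only child stays in the model but adds little about Week 4.

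**5. Selection.** Suppose a share s of the NT 201 arm is lost and would have scored d GICS points below those who stayed. The full-arm mean is then the stayers' mean minus s × d, so omitting them overstates the effect by s × d:

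- 2% × 2 = 0.04
- 5% × 2 = 0.10
- 10% × 3 = 0.30

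These compare with a planned 1.0 point; both s and d are assumptions. Selective placebo loss offsets this: the net error is (s × d on NT 201) − (s × d on placebo).

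**6. Replacement analyses.** With a share p lost in both arms, no-change replacement scales a 1.0-point difference to 1 − p: 0.95 at 5% (power 92.8%) and 0.90 at 10% (power 90.0%), SD held at 1.93. This assumes the lost children would have had average outcomes, so it measures dilution in a sensitivity analysis, not bias in the primary one.

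**The case against.** The best defence is that the protocol already keeps most of these children in view. AE withdrawals are followed to the end of the cycle, a span that includes Week 4. Section 10.1 times the final visit like V6, and V6 values enter the MMRM. SAP 7.1 analyses end-of-study efficacy in the extension whether or not the child stopped early, so efficacy data at a premature final visit are foreseen there. The eligibility checks in 7.4, which look back for severe related AESIs in any period, fit a reading in which some affected children are still on study at V6. Early leavers remain in the FAS and in the replacement analyses, and SAP 7.1.1 provides for conservative sensitivity analyses.

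Much of this stands, and it rules out several stronger readings:

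- A reader might infer that Week 4 data are lost whenever a criterion is met. The documents do not say so. They are silent on efficacy during follow-up, and Table 6 cannot be checked.
- A reader might infer that leaving before V3 always removes a child from the MMRM. It does so only if no later main-period value exists.
- A reader might take the sentence on missing values in 12.4.7.1 as false. It speaks of single missing values and claims nothing about children with none. Its remark on reasons for leaving is tentative and sits in an argument that assumes comparable percentages missing.
- A reader might infer that withdrawals will cluster before V3, because 6.2 says the effect builds over about two weeks. That describes onset of effect, not the timing of AESIs or withdrawals.

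The defence does not remove the gap. Follow-up for an AE is not a requirement to measure uSFR or GICS. Section 9.2 points to a final assessment on discontinuation, while 10.1 points to one at 16 ± 2 weeks. No rule in the available text maps an early main-period final visit to V3–V6.

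**Conclusion.** The point holds in a limited form. The AE and severe-AESI criteria end participation in a period with no further dose due, and no available text requires uSFR or GICS at V3–V5 afterwards. A child withdrawn before V3 may have no Week 4 co-primary value and, without a later main-period value, adds nothing to the primary MMRM despite being in the FAS.

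The number affected is probably small and no rate is given. The power cost is minor: about 1 percentage point at an assumed 5% loss in both arms and about 2 at 10%. What matters is selective loss of treated children by arm. Under the assumptions in the working, that could overstate the GICS effect by 0.04 to 0.30 points if only NT 201 is affected, and by less if placebo loses poor responders too. The change is worth making because it is cheap and because missed assessments cannot be recovered. The documents do not show that the primary analysis is invalid.

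**What to change.** In protocol 7.5.1 and 9.2, separate receiving no further injection from ending study participation. State that a child who will have no further injection after Day 1 for an AE, AESI or C-SSRS reason stays on the scheduled V3–V6 visits for efficacy: at least the carer GICS, and uSFR where the investigator finds it feasible. Except where consent or assent is withdrawn, and except in pregnancy, where 10.6 applies. Reconcile 7.5.1, 9.2 and 10.1 on when the final visit after discontinuation takes place.

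In the SAP:

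- state how an early final visit maps to V3–V6;
- specify before unblinding how values taken after prohibited anti-sialorrhea medication are handled. Protocol 3.3.4 allows such medication after discontinuation, so using every value as observed is an estimand choice to be made openly, whereas collecting the value is not in dispute;
- report by arm how many FAS children aged 6–17 have no V3 value.

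The cost is protocol wording, a few SAP sentences and a few extra efficacy assessments at visits that already exist. Children withdrawn for AEs are already followed to the end of the cycle. No stopping or re-injection rule changes.
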